5.4 Confidentiality

Patient records are maintained in strict confidentiality according to common clinical ethical usage and Federal and Texas state laws. Records are stored in high security areas in locked filing cabinets and are only accessible to professional personnel either associated directly with the study or with the need for emergency care on an after-hours basis. No records identifying the subject by name will be disclosed for any reason without specific execution of a written authorization by the patient. To protect confidentiality during data analysis and subsequent publication, database subjects will be identified only by lens group and an assigned confidential subject number.

5.5 Criteria for Discontinuing Contact Lens Wear

Lens wear will be discontinued by the patient on a temporary basis in accordance with the RSVP clinical rule (as defined above); and examined as soon as possible thereafter on a scheduled or 24-hour emergency basis. Following standard FDA contact lens protocol usage, an adverse reaction is defined as an unanticipated complication that might have been attributed to the use of the test lens or following testing (irrigation), and if untreated or ignored would have led to progressive or permanent reduction in visual acuity or resulted in sustained ocular damage; such occurrences will be reported promptly to the IRB and to the study sponsor.

In general, an adverse reaction, patient non-compliance, or patient choice will be the cause for discontinuance from the study. Major potential outcomes mandating discontinuance include:

2. The investigator will discontinue a patient at any time during the study for any reason if, in her opinion, it is in the best interest of the patient. The reason must be recorded.
3. A patient may voluntarily withdraw from the clinical trial for any reason. This reason must be recorded.
4. Discontinuation may be needed when the patient has not worn lenses for more than two days due to non-compliance.
5. Additionally, patients may need to be discontinued because of protocol deviations or because of lack of follow up or relocation. A patient is considered lost to follow up if a scheduled visit is missed and the patient is unresponsive to repeated attempts at rescheduling.
6. Patients will be discontinued if monitoring of the clinical trial reveals an unacceptable level of device related adverse events, even though some patients are not affected.

There are certain actions that are required for discontinued patients:

1. The investigator will perform an ocular examination and document the results and reason for discontinuation. Patients who have positive slit lamp findings that are at least one whole grade greater than baseline should be subsequently followed until their findings are stabilized and returned to baseline.
2. The investigational lenses must be retrieved from the patient. For relocated patients or those lost to follow up it must be documented that every attempt and effort was made to locate the patient and retrieve all investigational lenses.
3. Should a patient be discontinued because of an ocular complication or adverse reaction, visits must be documented until recovery of ocular health and full visual acuity has been achieved, if such can occur.

5.6 Safety Monitoring: Adverse Events

5.6.1 Serious Adverse Events

Any adverse event that is serious but not likely due to contact lenses, such as a retinal detachment or cardiac arrest, must be reported to the IRB and the study sponsor.

5.6.2 Adverse Device Effects (A.D.E.)

Adverse device effects are hazardous, sight-threatening conditions such as corneal ulcers, corneal abrasions > 2mm, corneal scarring, iritis, permanent loss of vision, and other ocular infections or inflammations. All grade 4 biomicroscopy findings, which could be associated with these conditions, are thus considered potential adverse reactions except grade 4 tarsal abnormalities.

Each potential adverse device effect must be reported by the investigator to the IRB immediately at [contact].

And submit within 3 working days:

- A potential adverse event form including detailed drawings
- CRP's, lenses worn and any solutions or lens cases that may have been used at the time
- Cover letter/report with diagnosis

To UTSWMC IRB

Then if the patient is discontinued – a written report is also required indicating the subsequent treatment and resolution of the condition for the patient's file.

5.6.3 Undesirable Side Effects (U.S.E.)

All grade 3 findings and grade 4 tarsal abnormalities are considered ocular complications. They are associated with non-sight threatening, reversible events that may require temporary discontinuation of lens wear, treatment, or additional follow-up visits. Examples include giant papillary conjunctivitis, marked dry eyes, blepharitis, allergic responses, and general irritation.

6.0 Data Management, Quality Assurance, and Analysis

Data management and quality assurance will be accomplished in the Department of Ophthalmology. Statistical analysis will be conducted in the Department of Biostatistics and Clinical Sciences at UTSWMC. [name], Director of Biostatistics, will serve as the biostatistical collaborator on this study.

6.1 Form Management

Data entry forms will be prepared and stored in the Department of Ophthalmology. Masters will be maintained on file with a complete packet issued at randomization for the patient's file. The patient's master file with copies of all encounters to date will be kept in a secured area in

the clinical research office to maintain confidentiality. Only single encounter forms needed for specific visits or tests will be taken to the clinic or laboratory for data recording. These will be returned to the master file the same day of completion.

6.2 Data Entry and Storage

Data entry will be accomplished in the Department of Ophthalmology upon completion of a visit. The patient's master file containing all completed forms will be kept in the clinical research office under secure conditions. Weekly backups will be completed for the entire database. In order to protect the confidentiality of patients, data access will be denied to all but authorized personnel. This will be achieved by a password system for the datasets. Further, patient names and other sensitive data will be encrypted on all storage media. To further ensure confidentiality, data collected within the laboratory and data sent to the biostatistician will all be numerically coded.

6.3 Data Quality Assurance

Range and validity checks will provide monitoring of the data entry process. Technical measurements will be subject to random personal spot-checks by the PI on a regular basis to ensure data accuracy. Since all personnel listed in the study are already fully trained and experienced in the routine clinical fitting and experimental methodology, significant errors in data determination are not anticipated. Reports of the data as entered will be printed so as to provide a visual check against the data entry forms. Periodic audits will be conducted by the PI and the study coordinator to compare data as entered in the database with those of the paper data entry forms. Discrepancies will be noted, corrected immediately, and reviewed for common error that may be avoided by future training.

6.4 Data Analysis Procedures

Data analysis will begin with the extraction of data from the master database in ophthalmology. Range and validity checks and determination of validity of missing values will be a first step in analysis. Patient confidentiality will be assumed during data analysis in that the patient names will not be used but will be numerically coded. Data will be analyzed using an intent-to-treat approach.

Continuous demographic and baseline characteristics will be compared between the DAILIES TOTAL1 and the ACUVUE TruEye using Student's t-tests or Wilcoxon rank sum tests. Categorical demographic and baseline characteristics will be compared between the DAILIES TOTAL1 and the ACUVUE TruEye using Fisher's exact tests or Chi-square tests.

Data analysis will be specific to the objectives outlined below:

1. The primary experimental objective of this study is to characterize the effect of the DAILIES TOTAL1 compared to a control, high oxygen permeable silicone hydrogel daily disposable contact lens, the ACUVUE TruEye, on corneal epithelial cell desquamation. This effect will be assessed using a standardized ocular irrigation technique to measure:
 - a. Rate of desquamation of corneal epithelial cells (cells/min).

In this cross-over trial, treatment effects and carryover effects on the rates of desquamation of corneal epithelial cells (cells/min) will be compared between two treatment groups using Student's t-tests in Rosner (2006), and ANOVA in Chow and Liu (2014). If the p-value is less than $\alpha=0.05$ for surface epithelial cell desquamation, then the surface epithelial cell desquamation is considered significantly different between the two groups.

References:

Rosner B. (2006) Fundamentals of Biostatistics, 6th Edition. Thomson-Brooks/Cole.

Chow S and Liu J. (2014) Design and analysis of clinical trials: concepts and methodologies, 3rd Edition. Wiley.

2. The secondary experimental objective of this study is to evaluate the effect of wear of the DAILIES TOTAL1 on the central corneal epithelium compared to a control, high oxygen permeable silicone hydrogel daily disposable contact lens, the ACUVUE TruEye. This effect will be assessed using IVCN to measure:
 - a. Area of surface epithelial cells within the central cornea (μm^2).

Same analytical methods as described above for the primary endpoint will be used for the analysis of the secondary endpoint.

3. Multiple exploratory aims will also be investigated. These aims will be used to evaluate the effects of lens wear on the biology of the limbal epithelium, lid wiper and changes in the extracellular tear content of DNA in response to wear of the DAILIES TOTAL1 compared to a control, high oxygen permeable silicone hydrogel daily disposable contact lens, the ACUVUE TruEye.

These will be assessed by:

- a. Area of surface epithelial cells within the limbal region.
- b. Thickness of the central and limbal epithelium.
- c. Dendritic cell infiltration in the limbal region.
- d. Staining of the lid wiper region with sodium fluorescein and lissamine green.
- e. IVCN evaluation of the lid wiper surface.
- f. Quantification of extracellular DNA adherent to the posterior lens surface and in the post lens tear film.

Exploratory data analysis will be conducted for the analysis of the above variables. Descriptive statistics will be computed and used for the estimation of the sample size needed for a future large trial if the study results look promising.

[name] will be responsible for the final review of data analysis.

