4.1.2 Baseline Visit

One month after completing a successful COE, being enrolled in the study and randomized to a test group, patients will be scheduled for a baseline visit to the contact lens clinic for dispensing the assigned test lenses. Test lenses and their properties are summarized in Table II.

Table II: Test lens properties

Test Lenses	Material	Water Content	Dk*	Dk/t**	Base Curve
DAILIES TOTAL1	Delefilcon A	33%	140	156	8.50 mm
ACUVUE TruEye	Narafilcon A	46%	100	118	8.50 or 9.00 mm

*Dk: oxygen permeability, unit: $\times 10^{-11}$ (cm²/sec)(mL O₂/mL mmHg)

**Dk/t: oxygen transmissibility, unit: $\times 10^{-9}$ (cm/sec)(mL O₂/mL mmHg)

At the baseline visit, all matters involving informed consent will be re-reviewed with the patient for the last time prior to lens fitting. The patient is given the opportunity to withdraw if desired.

4.1.2.a Brief pre-dispensing screening examination

Performed as for COE but Schirmer strip testing, IOP measurements and dilation are omitted

4.1.2.b Lens Fitting Procedures

- A Bausch & Lomb keratometer is used to measure the central corneal keratometry values in both eyes recorded to the nearest ¼ diopter (“K” value).
- Each eye will be trial fitted to ensure proper movement.
- Lenses will be checked for optimum comfort and final visual acuity (lens power).

4.1.2.c Lens Care Solutions

Since this trial is investigating daily disposable lenses, no lens care solutions will be required. Only preservative-free saline will be provided to rinse lenses prior to insertion.

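### Does the intent-to-treat statement need changing because participants may be discontinued for non-compliance and no analysis set or one-period rule is given?

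*Combined protocol and SAP*

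**What the plan says.** Section 6.4 gives the analysis principle in one sentence: "Data will be analyzed using an intent-to-treat approach". On missing data it provides only for a check of whether missing values are valid. For the primary endpoint, "treatment effects and carryover effects on the rates of desquamation of corneal epithelial cells (cells/min) will be compared between two treatment groups" by Student's t-tests and ANOVA, each given by textbook citation. For the secondary endpoint, "Same analytical methods as described above for the primary endpoint will be used for the analysis of the secondary endpoint".

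Section 5.5 governs departures. Its lead sentence reads: "In general, an adverse reaction, patient non-compliance, or patient choice will be the cause for discontinuance from the study". Two more specific items follow: "Discontinuation may be needed when the patient has not worn lenses for more than two days due to non-compliance" and "Additionally, patients may need to be discontinued because of protocol deviations or because of lack of follow up or relocation". For those who leave, "The investigator will perform an ocular examination and document the results and reason for discontinuation"; lens retrieval and, after a complication, recovery visits are also required. Irrigation and confocal microscopy are not on that list.

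On timing, Section 4.1.2 places randomisation before the washout and baseline: after "being enrolled in the study and randomized to a test group, patients will be scheduled for a baseline visit". Section 3.2 takes the biological outcomes only at Visits 2, 4, 5 and 7. Section 3.4.4 deals with dropout by recruiting 94, 47 per sequence, so that 84 finish. Section 4.3.2.c returns participants to the study once a lens problem has resolved.

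**The concern.** Intent-to-treat exists to stop participants being left out because of what happens after randomisation, adherence above all. Here adherence is itself a listed reason for leaving the study, and no outcome is required on leaving. A participant removed before Visit 4 has no evaluable period; one removed between Visits 4 and 7 has one. The plan does not say whether either belongs to the primary analysis. Nor does it say whether the crossover model uses complete pairs only or treats participants as random, so that single periods contribute.

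If wear depended on the lens, leaving out poor wearers could shift the lens contrast, and a report labelled intent-to-treat would not show it. The two-day trigger adds to the unease. It does not say whether the days are consecutive or total, and although Section 3.4.3 masks the observer doing irrigation and microscopy, nothing says the person deciding on discontinuation is masked.

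**Working it through.** **1. The plan's own figure.** Inputs from Section 3.4.4: difference 16.3 cells/min, SD 37, 84 subjects, 80% power, alpha 0.05. I take the test as two-sided and 37 as the within-participant SD, because that reading reproduces 84.

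- Standard error = 37 × √(2/84) = 5.71.
- Power from the noncentral t with 82 degrees of freedom = 80.6%; 84 is the smallest even number reaching 80%.
- 84/(1 − 0.10) = 93.3, rounded up to 94.

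The design is therefore sized on participants who complete both periods. A complete-pair analysis of 84 delivers the stated power. At 12% loss, 94 × 0.88 = 82.7, and power is 79.6% with 82 or 80.1% with 83.

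**2. How many are involved.** 10-12% of 94 is 9 to 11. The one-period rule matters only for those lost after Visit 4 (month 3 of 6 in Table 1): about 5 if loss is even over time, with a range of 0 to 11.

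**3. Effect of leaving out low wearers.** The planned 20% and 40% reductions with a difference of 16.3 imply a baseline of 16.3/0.20 = 81.5 and reductions of 16.3 and 32.6 cells/min. Assume a share f = 0.10 are low wearers whose reduction shrinks by a = 0.5 or 1. The documents give neither figure.

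| Low wear on | Difference in all randomised | a = 0.5 | a = 1 |
|---|---|---|---|
| Both lenses | 16.3(1 − fa) | 15.5 | 14.7 |
| TruEye only | 32.6(1 − fa) − 16.3 | 14.7 | 13.0 |
| TOTAL1 only | 32.6 − 16.3(1 − fa) | 17.1 | 17.9 |

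With these participants left out the difference is 16.3. The shifts run from 0.8 to 3.3 cells/min, or 0.1 to 0.6 of the 5.71 standard error. The top value needs one participant in ten to show no reduction at all, and only on TruEye.

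**4. Complete pairs or random participants.** If all 10 non-completers gave a first-period value and a mixed model used it, power would rise from 81.5% to between 82.1% and 83.6% (normal approximation; between-period correlation 0.7 down to 0, assumed). In simulation (47 per sequence, 5 or 10 lost after Visit 4, loss unrelated to response, intraclass correlation 0.3 to 0.5 assumed), neither form was biased. Their verdicts differed in 2.6 to 4.7% of trials at the planned effect. Picking the better of the two added 0.5 to 0.9 points to the type I error.

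Bias in the complete-pair form needs loss that is both related to response and uneven between sequences. With 5 lost after Visit 4 from the lower half of responses (plus 5 before it), the bias was 0.7 to 1.0 cells/min for a 4/1 split and 1.3 to 1.5 for 5/0, at most 1.5/5.71 = 0.26 standard errors. By chance, a split of 4/1 or worse has probability 2 × (5 + 1)/32 = 0.375, and 5/0 has 2/32 = 0.06.

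**5. The two-day trigger.** Take 60 wear days per period and a 1% daily miss rate, both assumed. If missed days are independent, P(more than 2 of 60) = 0.0224, so 1 − (1 − 0.0224)² = 4.4% exceed two days in total in at least one period, against about 0.02% for a run of three. If the chance of missing a day after a missed day is 0.5, the figures become 16% and 14%. The apparent importance of the consecutive-or-total question is thus largely a product of the independence assumption. The trigger also says only that discontinuation may be needed, and only for non-compliance, so none of these percentages is a forecast of removals.

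**The case for a change.** The best case for a change is that a label cannot supply data that were never collected. If participants are taken out for poor adherence and not measured, no analyst can recover the as-randomised effect, and the words in Section 6.4 overstate what is estimated. Comfort is the test lens's advertised advantage (Section 1.1), so adherence might differ by lens. Reinstatement under Section 4.3.2.c covers resolved lens problems, not non-compliance. The remedy would be mostly wording.

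Part of this stands: the label and the discontinuation rules do not fit neatly, and the one-period rule is unstated.

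The rest is weaker. The two specific items in Section 5.5 are permissive, and the lead sentence is qualified as general. Its list of required actions concerns safety and lens retrieval and does not exclude an outcome measurement. Participants who miss a day or two, or wear lenses outside the 8 to 12 hours of Section 4.1.3.b, need not leave. A promise of comfort is not evidence that non-compliance differs by lens, and losses during the first washout precede any study lens. Section 6.4 names t-tests and ANOVA, not a mixed model, so the plan itself points towards complete pairs. Seeking outcomes from those removed could also carry a cost, since Section 4.1.1.a excludes termination for non-compliance from its protection of benefits.

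**Conclusion.** No change to the plan follows. No stated number or test is shown to be wrong. The gap can be filled in the ordinary way: analyse participants by randomised sequence, use those with both periods in the crossover tests, say so, and report losses with the reasons that Section 5.5 already has recorded. For hypotheses about epithelial change following lens wear (Section 1.2), an as-worn effect in completers is defensible. An as-randomised effect is also defensible, but it could cost power: with all 94 analysed, 81%, 77% or 67% at differences of 15.5, 14.7 or 13.0 cells/min. Neither model form is better under every loss mechanism.

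On the plan's figures, 9 to 11 of 94 participants are involved, the stated power holds at 84 pairs, and any shift is about 0.1 to 0.6 standard errors under the assumed low-wear share and shrinkage. The actual bias cannot be determined from the documents and is probably small.

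The headcounts assume 94 recruited. Sections 3.1, 3.3 and 3.4.4 also give 140, a separate inconsistency. At 10-12% loss, 140 would leave 123 to 126 completers (140 × 0.88 = 123.2; 140 × 0.90 = 126). Only if 140 were randomised and just 84 finished would 56 participants (40%) lack a stated place, and this conclusion would then need another look.

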1.2 Test Hypotheses

This proposal will test the primary hypothesis that:

- A. The magnitude of the reduction in corneal epithelial surface cell exfoliation following wear of the new DAILIES TOTAL1 water gradient lens will be less than the magnitude of the reduction measured following wear of a control, high oxygen permeable silicone hydrogel daily disposable contact lens.

This proposal will test the secondary hypothesis that:

[figure not shown]
- A. The area of corneal surface epithelial cells will not be increased over baseline following wear of the new DAILIES TOTAL1 water gradient lens while the area of corneal surface epithelial cells will be increased following wear of a control, high oxygen permeable silicone hydrogel daily disposable contact lens.

This proposal will test the following exploratory hypotheses:

- A. There will be an improvement in the biology of the lid wiper region following wear of the new DAILIES TOTAL1 water gradient lens when compared to a control, high oxygen permeable silicone hydrogel daily disposable contact lens.
- B. Surface area of limbal epithelial cells will be unchanged following wear of the new DAILIES TOTAL1 water gradient lens, whereas area will be increased following wear of a control, high oxygen permeable silicone hydrogel daily disposable contact lens.

- C. Limbal and central epithelial thickness will be unchanged following wear of the new DAILIES TOTAL1 water gradient lens, whereas thickness will be reduced following wear of a control, high oxygen permeable silicone hydrogel daily disposable contact lens.
- D. Dendritic cell infiltration in the limbal region will be unchanged following wear of the new DAILIES TOTAL1 water gradient lens, whereas dendritic cell infiltration will be increased following wear of a control, high oxygen permeable silicone hydrogel daily disposable contact lens.
- E. Extracellular DNA content of tear fluid will be unchanged following wear of the new DAILIES TOTAL1 water gradient lens, whereas DNA content will be increased following wear of a control, high oxygen permeable silicone hydrogel daily disposable contact lens.

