3.0 STUDY DESIGN

3.1 Overview

This is a prospective, single center, randomized, bilateral crossover, dispensing clinical trial to evaluate the effects of the water gradient lens, DAILIES TOTAL1, on the biology of corneal epithelium over two months of daily wear compared to wear of a control high oxygen permeable silicone hydrogel daily disposable contact lens, the ACUVUE TruEye; and to correlate these changes with alterations in the lid wiper, tear film and cellular changes at the limbus. The total proposed duration of this study is 12 months to ensure enrollment of up to 140 established contact lens wearers, with anticipated completion of 84. Data will be collected at

baseline and following 2 months of daily wear for each lens type. Based upon data from our previous contact lens clinical trials, a 1 month washout period is required prior to initiating lens wear to eliminate any potential residual solution or lens effects on the corneal epithelium and restore homeostasis. The study is scheduled to commence upon IRB approval.

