3.2 Study Workflow

Visit 1: Comprehensive ocular examination (Contact Lens Clinic at UTSW)

- a. Informed consent reviewed and signed
- b. Comprehensive examination
- c. Back-up glasses ordered as needed
- d. Lens fitting and ordering based on randomization into the following lens groups:
 - i. Alcon DAILIES TOTAL1
 - ii. Johnson and Johnson ACUVUE TruEye
- e. One month washout begins immediately or after the participant obtains the spectacles.

Visit 2: Baseline Visit, lens 1 dispensed (+/- 3 days)

- a. Brief screening exam
- b. Informed consent re-reviewed
- c. Baseline biological indicators (outcome measures) assessed
 - i. Tear collection OU
 - ii. Lid wiper staining OD
 - iii. Ocular irrigation OS
 - iv. Confocal microscopy of cornea, limbus and lid margin OD
- d. Lenses dispensed

Visit 3: 1 week of lens wear (+/- 3 days)

- a. Contact lens check up
 1. Snellen Visual Acuity Testing
 2. Lens fitting
 3. Slit lamp examination without corneal staining

Visit 4: 2 month of lens wear (+/- 3 days)

- a. Brief screening exam
- b. Lenses and diaries collected
- c. Biological indicators assessed
 - i. Lenses collected OU
 - ii. Tear collection OU
 - iii. Lid wiper staining OD
 - iv. Ocular irrigation OS
 - v. Confocal microscopy of cornea, limbus and lid margin OD
- d. Patient begins next 1 month washout period

Visit 5: Baseline visit, lens 2 dispensed (+/- 3 days)

- a. Brief screening exam
- b. Baseline biological indicators assessed
 - i. Lenses collected OU
 - ii. Tear collection OU
 - iii. Lid wiper staining OD
 - iv. Ocular irrigation OS
 - v. Confocal microscopy of cornea, limbus and lid margin OD
- c. Lenses dispensed – begin crossover phase

Visit 6: 1 week of lens wear (+/- 3 days)

- a. Contact lens check up
 - i. Snellen Visual Acuity Testing
 - ii. Lens fitting
 - iii. Slit lamp examination without corneal staining

Visit 7: 2 month of lens wear (+/- 3 days)

- a. Brief screening exam
- b. Lenses and diaries collected
- c. Biological indicators assessed
 - i. Lenses collected OU
 - ii. Tear collection OU
 - iii. Lid wiper staining OD
 - iv. Ocular irrigation OS
 - v. Confocal microscopy of cornea, limbus and lid margin OD
- d. Study completed

Table 1: Overall study design

Visit No.	Interval	Time in lens	Procedures
1	0	0	Sign and review IC. Comprehensive ocular examination. Order back-up glasses if needed. Lens fitting and ordering. One month washout period of no lens wear.

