3.3.1 Inclusion/Exclusion Criteria

For inclusion in this study, subjects must be:

- Aged 18-38 years
- Any sex, race or national origin accepted as with our past studies. Minority representation will be proactively encouraged
- Sign written informed consent
- A habitual contact lens wearer and only wear lenses for daily wear use (no overnight wear) or non-contact lens wearers wanting to try contact lenses
- Myopia range: -1.00 to -6.00 with regular astigmatism ($\leq 1.00D$, both eyes)
- Be willing to wear spectacles for two 1-month washout periods
- Have acceptable fit with test lenses and be willing to wear lenses for the duration of the study.
- Need correction in both eyes and be correctable to within 3 letters (high contrast Snellen VA) of their current contact lens prescription at baseline in each eye with the test lenses.
- No history of allergic eye disease either seasonal or associated with previous contact lens wear.
- A routine screening complete ocular examination (COE) with ocular findings considered to be within normal limits.
- Be willing and able to follow instructions regarding the wear of the daily disposable lenses and attend the scheduled follow-up visits.
- Must be able to arrange weekday appointments between 8:00 AM and 12:00 PM.

Exclusion criteria include:

- Habitual lens wearers unable to wear lenses for a minimum of 8 hours per day.
- Use of concurrent ocular medication
- Habitual toric or bifocal contact lens wearers
- Any previous history of keratorefractive surgery or recent ocular injuries or ocular surgery within the prior 3 months
- Any preexisting ocular disease
- Monocular contact lens wear
- Any systemic disease or ocular abnormality that may impact optimal contact lens wear

-
- Use of systemic medications including but not limited to antihistamines, corticosteroids, anticholinergics or immunomodulatory agents
 - Pregnancy or lactation
 - Concurrent enrollment in another clinical trial

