3.4.4 Sample Size Determination and Statistical Methods

A total of 140 patients will be recruited for this study. Sample size calculations (detailed below) and statistical methods to detect significant changes in the outcome measures were derived from our previous studies evaluating the effects of silicone hydrogel lens wear on the corneal epithelium (Ladage et al, *Ophthalmology* 2001; 108: 1279-1288 and Robertson et al, *IOVS* 2008; 49: 7-15). The magnitude of change for of all outcome measures will be simultaneously compared between lens types using a Type I error rate of $\alpha=0.05$. Statistical analysis will be completed in the Department of Clinical Sciences and Biostatistics at UTSWMC.

A. Surface epithelial cell desquamation

Surface epithelial cell desquamation is the most sensitive and reliable predictor of epithelial perturbation in response to contact lens wear. In our prior studies, silicone hydrogel lens wear worn in a daily modality reduced corneal surface epithelial cell desquamation by 40-50%. We hypothesize that the impact on epithelial shedding rate (cells/minute) will be less following wear of the Dailies Total 1 ($\Delta \leq 20\%$ reduction) compared to wear of a standard silicone hydrogel daily disposable, the ACUVUE TruEye ($\Delta \geq 40\%$ reduction). Assuming a difference in means between the two test lenses of 16.3 cells/minute and a standard deviation of 37 cells/minute, a total sample of 84 subjects in a 2x2 cross-over design will have 80% power at a significance level of $\alpha=0.05$.

B. Drop outs

Additional subjects were added to compensate for the potential dropouts to satisfy the requirements for completion of the 6 month study. Based upon our previous clinical trials, we anticipate a dropout rate of 10-12%. In the absence of time, cost, and ethical concerns, Guo et al. (2013) suggested choosing the largest sample size to guarantee power for all 2 tests. Therefore, we will recruit a total of 94 subjects for this cross-over trial. That is, 47 subjects will be allocated to each sequence in this 2x2 cross-over trial.

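### Do the between-lens baseline tests, and the lack of a planned Visit 5 versus Visit 2 comparison, leave the crossover's washout unchecked in a way that needs a change?

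*Combined protocol and SAP*

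**What the plan says.** Section 6.4 (Data Analysis Procedures) states "Continuous demographic and baseline characteristics will be compared between the DAILIES TOTAL1 and the ACUVUE TruEye using" Student's t or Wilcoxon rank sum tests, with Fisher's exact or chi-square tests for categorical variables. It names neither the visit nor the randomised sequences.

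For the primary endpoint the same section says "treatment effects and carryover effects on the rates of desquamation of corneal epithelial cells (cells/min) will be compared between two treatment groups", by the t-tests and ANOVA of two cited textbooks. It applies the same methods to the secondary endpoint, central corneal surface cell area.

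On design, Section 3.1 says that "a 1 month washout period is required prior to initiating lens wear to eliminate any potential residual solution or lens effects", and rests the length on earlier trials. Section 3.2 lists outcome measurements before each lens: at Visit 2, and again at "Visit 5: Baseline visit, lens 2 dispensed (+/- 3 days". At Visit 1 it has "Lens fitting and ordering based on randomization into the following lens groups". Section 4.2 randomises to two sequences.

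Part of the secondary hypothesis in Section 1.2 is within-lens: "The area of corneal surface epithelial cells will not be increased over baseline following wear of the new DAILIES TOTAL1 water gradient lens". The sample size in Section 3.4.4 rests on this: "Assuming a difference in means between the two test lenses of 16.3 cells/minute and a standard deviation of 37 cells/minute".

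**The concern.** Two things look wrong.

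First, if the baseline groups are defined by lens worn, almost every subject is in both groups. A demographic comparison is then empty apart from dropouts. The measured baselines are paired, so an independent-sample test is too conservative and could miss a real imbalance.

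Second, the design relies on washout, yet nothing planned compares Visit 5 with Visit 2. The usual carryover test compares sequences, so it cannot see a residual that both lenses leave alike, and it has little power for one that differs. If surface cells were still enlarged at Visit 5, the increase measured from that baseline would shrink towards zero. That would favour the statement that DAILIES TOTAL1 does not increase cell area.

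At stake would be the reading of within-lens changes from baseline, and confidence in the washout.

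**Working it through.** **Inputs.** From Section 3.4.4: difference 16.3 and SD 37 cells/min, 84 completers, 80% power, alpha 0.05, with reductions of 20% and 40%. Assumed: two-sided tests, 42 completers per sequence, and within-subject correlation 0.3, 0.5 or 0.7 (the documents give none). Power is from the noncentral t distribution.

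**1. The plan's own figure.** If 37 is the within-subject SD of the analysed quantity, SE = 37 × √(2/84) = 5.71, 16.3/5.71 = 2.85, and power on 82 df is 80.6%. The stated 80% reproduces. If 37 were the SD of the paired difference, SE = 37/√84 = 4.04 and power would be 97.9%. So 37 is a within-subject SD. The text does not say whether it belongs to a single reading or to a change score, and both give 80.6%.

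**2. Which groups do the baseline tests compare?**
- Section 3.2 has lenses fitted at Visit 1 according to a randomised lens group.
- Section 3.4.2 randomises subjects to one lens or the other, then crosses them over.
- Sections 4.1.1.c and 4.1.2 speak of randomisation to a test or control group.

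Throughout, a lens group means the lens assigned first. On that reading the groups are independent and the named tests are valid. On the by-lens reading, the approximate true size of a nominal 5% test is 2 × [1 − Φ(1.96/√(1 − ρ))]: 1.9%, 0.6% and 0.03% for ρ = 0.3, 0.5 and 0.7. Simulation gives 2.0%, 0.6% and 0.04%. These sizes matter only on the less likely reading, and Section 6.4 attaches no decision to the result.

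**3. What a common residual does to the lens contrast.** A 20-point gap worth 16.3 implies a baseline of 16.3/0.20 = 81.5, with reductions of 16.3 (DAILIES TOTAL1) and 32.6 (ACUVUE TruEye). Suppose Visit 5 is still c too low after either lens and post-wear levels are unaffected.
- DAILIES TOTAL1 first: measured reductions 16.3 and 32.6 − c; difference 16.3 − c.
- ACUVUE TruEye first: measured reductions 16.3 − c and 32.6; difference 16.3 + c.
- Average over sequences: 16.3, for any c.

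Each lens's own mean reduction falls by c/2. With c = 8.15 they become 12.2 and 28.5; with c = 16.3, 8.2 and 24.5. The lens difference is 16.3 every time. The same cancellation holds for cell area. If end-of-wear rates are analysed instead, an equal carryover is simply a period effect and cancels too.

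**4. What the extra comparison could show.** For Visit 5 minus Visit 2 in 84 completers:

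| | 37 = within-subject SD of one reading | 37 = within-subject SD of a change score |
|---|---|---|
| SD of the difference | 37√2 = 52.3 | 37 |
| SE overall | 5.71 | 4.04 |
| 95% CI half-width (t = 1.989, 83 df) | 11.4 | 8.0 |
| Power, common residual 16.3 | 81% | 98% |
| Power, common residual 8.15 | 29% | 51% |
| Power, residual differing by 16.3 between sequences | 29% | 51% |

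The planned carryover test is also weak for a 16.3 differential residual. On subject totals its power is 18%, 13% or 9% for ρ = 0.3, 0.5 or 0.7 if 37 is the within-subject SD of a reading, and 24%, 21% or 19% if 37 is the total SD of a reading. On totals of change scores it is 17% (37 for one reading) or 29% (37 for a change score).

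**The case for a change.** The best case for a change is that it costs almost nothing. One table from data already scheduled would let readers see whether shedding and cell area had returned to their Visit 2 level. In a simulation with ρ = 0.5 and a residual of 16.3 common to both lenses, the carryover test rejected in 4.8% of trials, its false-positive rate, while a paired Visit 5 versus Visit 2 test rejected in 98%. The secondary hypothesis is worded partly within-lens, and so are exploratory hypotheses B to E.

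Some of this stands. The plan contains no Visit 5 versus Visit 2 comparison, the carryover test cannot reveal a common residual, and Section 6.4 could have named the sequences.

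The case for requiring a change does not stand. A null difference would not establish adequate washout: the difference also contains any period effect, and in habitual wearers Visit 2 itself follows one month without lenses, so an equal residual there cancels. Section 3.1 describes the participants as established wearers. The informative subset, "or non-contact lens wearers wanting to try contact lenses", is of unknown and possibly small size. The within-lens harm also falls on an analysis that is not planned, because Section 6.4 tests the secondary endpoint between lenses and treats the exploratory aims descriptively. Whether a within-lens test ought to exist is a separate matter.

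**Conclusion.** No change is needed. The baseline wording is a gap that an analyst would fill sensibly by tabulating demographics and Visit 2 values by randomised sequence; on that reading the named tests are valid and feed no decision. Carryover is already to be analysed for the primary and secondary endpoints, although with low power (9% to 29% for a differential of 16.3 across the assumptions above). A residual common to both lenses shifts the planned between-lens estimate by 0 and each lens's descriptive change by c/2.

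An added Visit 5 minus Visit 2 summary with a confidence interval would be good descriptive practice. It would alter no estimate, p-value or sample size, and it could not confirm the washout. Its precision (half-width 8.0 or 11.4 cells/min) turns on an SD whose type the plan does not state, so no fixed power figure belongs in the SAP.

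This conclusion assumes that lens groups mean the first assigned lens, that the lens effect is averaged over the two sequences, and that within-lens changes stay descriptive as Section 6.4 has them. Nothing in the documents suggests incomplete washout, but the earlier trials behind the one-month choice cannot be checked here.
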